### 1.3.2 Potential Benefits

In addition to the equivalent level of risk anticipated, the use of the Et Control option has the potential to improve the clinical workflow for the clinician during a procedure and potentially present some additional safety mitigations.

**Study Title:** Multi-site Anesthesia randomized controlled Study of End tidal control (Et Control) compared to conventional anesthesia Results (MASTER-Anesthesia Trial)  
**Study No:** 123.07-2015-GE5-0002

GE Healthcare

Several potential benefits for the clinician and subject have been considered and are discussed below.

The Et Control option is designed to help simplify the workflow for the clinician during an anesthetic case. Et Control may help minimize the number and frequency of clinician interactions with the Aisys CS user interface needed to target and maintain a desired anesthetic agent concentration and flow range for the subject. This can potentially allow the clinician to dedicate greater attention to the subject. During an anesthesia case, the clinician must monitor, manage, and control a multitude of complex parameters, constantly assessing the changing status of the patient and making adjustments to optimize care and maintain safety. This includes, among many things, analyzing and compensating for differences between the targeted and the delivered agent and oxygen concentrations. Et Control was designed with a thorough understanding of this complexity and the human factors involved.

Et Control allows the clinician to directly set the appropriate EtAA and EtO2 for the subject based on his or her clinical judgment and the dosing detailed in the drug package insert. The drug labeling describes dosing guidance in terms of minimum alveolar concentration or MAC (based on EtAA), and Et Control was designed to further enhance the clinician's ability to directly target to the desired levels. With direct setting of end tidal targets and constant monitoring of the subject's end tidal levels, Et Control has the potential to improve the accuracy of, reduce deviation from, and responsiveness to achieve intended gas-mixture delivery to the subject, potentially reducing inadvertent over or under-shoot or setting errors. This can also help simplify the delivery and maintenance of desired concentrations throughout the broad range of total flows currently used in clinical practice, from 0.5 liters per minute (lpm) up to 6 lpm.

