These two primary endpoints, along with the secondary efficacy endpoints (response time, setting time, overshoot amount), are chosen to assess the capability of Et Control in achieving and maintaining the end tidal concentration of anesthetic agent and oxygen.

This study is designed to demonstrate that Et Control is non-inferior to the control device in maintaining end tidal anesthetic agent (EtAA) and end tidal oxygen ( $EtO_2$ ) concentrations by a margin of 5%.

The hypotheses for the primary endpoints are:

$$H_0: \mu_{\text{et}} - \mu_{\text{con}} < -5\% \text{ vs } H_1: \mu_{\text{et}} - \mu_{\text{con}} \geq -5\%$$

for both EtAA and  $EtO_2$ , where  $\mu_{\text{et}}$  is the average percent duration of Et Control with EtAA and  $EtO_2$  maintained within the acceptable range, and  $\mu_{\text{con}}$  is the average percent duration of control device with EtAA and  $EtO_2$  maintained within the acceptable range.

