#### **8.1.4 Analysis of Secondary Endpoints**

##### **8.1.4.1 Performance Statistics**

For response time, settling time and overshoot amount (% to steady state mean for anesthetic agent, and v/v for O2), analysis will be on the basis of each steady state. The arithmetic average of all steady states will be calculated and be compared between the Et Control Arm and the Control Arm using t-test. Subjects with at least 1 overshoot amount greater than 10%, 20%, or 30% of steady state concentration will be counted and compared between the two arms using Fisher exact test.

For average deviation (% to steady state mean for anesthetic agent, and v/v for O2) and half width of 95% CI of deviation, analysis will be on the basis of each subject. The weighted average using the duration of steady state duration as the weight for a subject will be calculated and compared between the Et Control and Control Arms using t-test. For the maximum deviation (% to steady state mean for anesthetic agent, and v/v for O2), the maximum of all steady states for a subject is taken for analysis, and the maximum deviation be compared between Et Control and Control arms using nonparametric Wilcoxon rank sum method.

The analysis of above performance statistics will be performed by different ASA status.

**Study Title:** Multi-site Anesthesia randomized controlled Study of End tidal control (Et Control) compared to conventional anesthesia Results (MASTER-Anesthesia Trial)  
**Study No:** 123.07-2015-GES-0002

GE Healthcare

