## APPENDIX 2 – EXTRACTION ALGORITHM

A high level description of the extraction algorithm is provided below. The extraction algorithm is common to both operational modes (Et Control and Control) for the derivation of user desired end-tidal concentrations for anesthetic agent or oxygen. In addition to derived user desired end-tidal concentrations with the algorithm, the clinicians also record desired end-tidal concentration values during the case. The extraction algorithm analyzes the end tidal oxygen performance separately from the end-tidal anesthetic agent performance.

Although this extraction algorithm provides an objective comparison between Et Control and Control group, it cannot be used as an engineering analysis of the Et Control controller. The biggest reason for this is described in Step 4 (below). Instead of analyzing all of the Et Control set target end-tidal values directly, smaller setting changes are combined and treated as one step change. This combination of setting changes leads to a more conservative assessment of Et Control.

The extraction algorithm steps are as follows:

- 1) Identify all device setting changes. The device setting changes in the Fresh Gas control mode are the total mixer flow, mixer oxygen concentration and vaporizer concentration settings. Any mixer and vaporizer setting changes are interpreted as a user attempt to alter the patient end tidal agent or oxygen concentration. In the Et Control mode, patient end tidal concentration is targeted directly by adjusting the set end tidal agent and oxygen concentration. Et Control commands the changes to the mixer and vaporizer to alter the patient end tidal concentrations.
- 2) Determine whether a device setting change is 'Significant' in magnitude. The criteria for significance is whether the subsequent measured response 2 minutes following the device setting change causes a 0.9 %v/v, 0.31 %v/v or 0.17 %v/v change for Desflurane, Sevoflurane or Isoflurane, respectively, or 5 %v/v for oxygen.
- 3) Identify all periods of end tidal concentration measurement stability, following setting changes (i.e. Steady States). A stable period for agent is defined as all points where the rate of change of measured EtAA is less than 0.2 %v/v per minute and persists for a period of 2 minutes. A stable period for oxygen is defined as all points where the rate of change of the measured EtO2 is less than 1.5 %v/v per minute and persists for a period of one minute.

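### The Fisher comparison of subjects with at least one large overshoot takes no account of how many steps each subject contributes, and the plan has no per-step overshoot rate beside it

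*Combined protocol and SAP*

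**What the plan says.** Section 8.1.4.1 treats overshoot in two ways. For the amount: "The arithmetic average of all steady states will be calculated and be compared between the Et Control Arm and the Control Arm using t-test". For large overshoots the unit is the subject: "Subjects with at least 1 overshoot amount greater than 10%, 20%, or 30% of steady state concentration will be counted and compared" by Fisher exact test. The section does not adjust this count for the number of steps per subject, and it does not ask for step counts by arm.

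Section 3.4.1 says that the primary endpoints together with response time, settling time and overshoot amount "are chosen to assess the capability of Et Control in achieving and maintaining the end tidal concentration".

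Steps are defined in two scenarios (3.4.2 and 8.1.2). In scenario 1 the extraction algorithm of Appendix 2 starts from device setting changes: "The device setting changes in the Fresh Gas control mode are the total mixer flow, mixer oxygen concentration and vaporizer concentration settings". In Et Control mode the setting changes are those to the end-tidal agent and oxygen targets. Steps 2 and 4 of Appendix 2 then keep only changes followed by a significant measured response and merge the rest. In scenario 2 the Control Arm uses clinician-recorded targets and the Et Control Arm uses the set targets. Section 8.3 leaves out data where a clinician-recorded target is missing.

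**The concern.** A yes/no outcome of at least one event per subject mixes two things: how often a step overshoots, and how many steps there were. Only the first describes how well concentrations are controlled. If the arms contribute different numbers of steps, the Fisher test can favour the arm with fewer steps although a single step is no more likely to overshoot in one arm than in the other.

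There are structural reasons why the counts might differ. In scenario 1 the candidate changes come from different controls in the two arms. In scenario 2 the missing-target rule can remove data in the Control Arm and has no counterpart for targets logged by the machine. These could act in opposite directions.

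At stake is the reading of a secondary performance result in a study meant to support a marketing application (section 3.1). It could be taken as evidence of better control when it reflects the number of opportunities. For adverse events, section 8.1.7 analyses an event rate beside the percent of subjects affected. For overshoot above a threshold there is no rate.

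**Working it through.** **The plan's own figure.** The documents state no figure for the overshoot comparison. The only planned figure used here is the sample size in Table 8-1. With margin 5, expected difference +3 (90 v 87), SD 16, one-sided alpha 0.025 and power 0.95, the two-sample t-test needs 105 per arm; 105/0.85 = 123.5, so 124, as stated. The 124 therefore includes the 15% dropout allowance, and 105 is the number without it.

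**Inputs assumed.** Steps per subject (k) and overshoot risk per step (p) are not in the documents. I take k = 4 in one arm and 4 to 8 in the other, and p from 0.02 to 0.20, equal in both arms. Steps are treated as independent. Positive correlation within a subject would make the share with at least one overshoot rise more slowly with k, and so weaken the effect.

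**Formula.** P(at least one) = 1 − (1 − p)^k. For p = 0.10:
- k = 4: 1 − 0.9^4 = 0.344
- k = 5: 1 − 0.9^5 = 0.410
- k = 6: 1 − 0.9^6 = 0.469
- k = 8: 1 − 0.9^8 = 0.570

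**Fisher rejection at two-sided 0.05, 124 per arm, by exact enumeration, equal risk per step:**

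| Steps | p = 0.02 | p = 0.05 | p = 0.10 | p = 0.20 |
|---|---|---|---|---|
| 4 v 4 | 2.6% | 3.4% | 3.7% | 3.5% |
| 4 v 5 | 4.9% | 9.4% | 15.4% | 22.8% |
| 4 v 6 | 11% | 27% | 46% | 65% |
| 4 v 8 | 35% | 74% | 93% | 99% |

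With 105 per arm and p = 0.10, the figures are 13.7% (4 v 5), 40% (4 v 6) and 88% (4 v 8). When the arms have equal step counts there is no excess.

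**Which replacement test is safe.** I simulated per-subject proportions of steps with overshoot, with equal risk per step, 124 per arm and 4 v 8 steps (4,000 runs). The Wilcoxon test rejected in 32%, 42% and 32% of runs for p = 0.02, 0.05 and 0.10. The t-test rejected in 6%, 5% and 5%. Wilcoxon fails because the share of subjects with a proportion of exactly zero still depends on the number of steps. The t-test compares means, which do not.

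**The case against.** **No imbalance is shown.** This stands. A reader might infer that the plan expects step counts to differ, because section 1.3.2 says that "Et Control may help minimize the number and frequency of clinician interactions". The documents do not support that reading: interactions are not steps. Appendix 2 applies the same measured-response thresholds in both arms and merges non-significant changes, and the feasibility study found 26 v 26 interactions (section 1.2.3). The 6.7 v 15.2 adjustments per hour in section 1.1.4 come from another machine and also count settings. Equal interactions do not establish equal steps either; the question is open.

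**Maximum deviation.** Because section 8.1.4.1 says "the maximum of all steady states for a subject is taken for analysis", a reader might infer that this comparison also grows with the number of steady states. That is not supported. Deviation is measured within each steady state, so dividing a similar total time into more states need not raise the maximum. With 900 simulated breaths of identical noise split into 4 v 8 states, the median maximum was 3.35 v 3.35 SD (independent breaths), 3.03 v 2.92 (autocorrelation 0.9) and 2.31 v 2.07 (0.98): flat or lower with more states.

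**Other summaries exist.** The same section compares mean overshoot, and for average deviation "The weighted average using the duration of steady state duration as the weight for a subject will be calculated". Neither grows mechanically with the count. This limits the harm, but a mean does not say how often a large overshoot occurs.

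**The count is a legitimate outcome.** If one mode needs more significant steps, its patients do face more chances to overshoot. This stands as a patient-level outcome, and is why the count should be kept. It is not a measure of control per step.

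**Low stakes.** The comparison is outside the ordered tests (8.1.2) and the pass criterion (8.4), and no claim is announced for it. This stands and sets the rank of the point.

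**Conclusion.** The point holds as a conditional one. The at-least-one comparison is not adjusted for the number of analysed steps, so if step counts differ by arm it can be significant with equal overshoot risk per step. Under an assumed 10% risk and 124 per arm, one extra step on a base of four raises the rejection rate from about 4% to about 15%, and two extra steps raise it to about 46%. At a 2% risk the same two imbalances give 5% and 11%. All of these rest on assumed step counts, assumed risks and independent steps; the documents do not show whether an imbalance exists or which arm it would favour. The primary conclusion is unaffected. This is a minor point and a cheap improvement.

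**What to change.** In section 8.1.4.1:
- Keep the count of subjects with at least one overshoot above 10%, 20% or 30% as the patient-level summary.
- Report analysed steps, steady states and steady-state time per subject by arm, for each scenario.
- Add a between-arm comparison of the per-step overshoot rate at each threshold, using a logistic GEE on steps clustered by subject, or a t-test (not Wilcoxon) on per-subject proportions.
- State that any conclusion about control capability from the threshold analysis rests on this rate.

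The cost is SAP wording and one added table from data already extracted. Proportions from subjects with few steps will be noisier.

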### 6.1.1 Investigational Et Control Arm

The subjects assigned to this group are induced and their airway secured based on each investigator's conventional intravenous induction and intubation practice. Machine log data are collected when the investigator initiates the start of anesthesia case on the Aisys CS.

The investigator will initiate Et Control after the airway is secured (intubation) and mechanical ventilation is initiated. Machine log data is collected when the investigator initiates the start of anesthesia case on the Aisys CS. Adjustments to the anesthesia machine settings, discontinuation of use of the investigational Et Control option, and changes to treatment are based upon clinician judgment for the wellbeing of the subject. This protocol does not in any way instruct the clinician to make any dosage changes or adjustments for study purposes. All dosage decisions are based on their normal clinical practice.

Aisys CS machine log data collection will end when an "end case" is confirmed on the Aisys CS at the end of the anesthesia case. Evaluable Aisys CS data ends when the patient is finally disconnected from the Aisys CS breathing system.

The clinician must continuously monitor measured inspired and end tidal oxygen and anesthetic concentrations to assess individual responses and compare to the target concentrations.

The clinician must maintain adequate ventilation to deliver appropriate oxygen and anesthetic agent to the patient. Et Control does not adjust ventilator parameters.

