### 6.2.2 Maintenance Phase

The maintenance phase will start when mechanical ventilation is turned on and remains on for 10 breaths. Once the clinician starts mechanically ventilating the subject, he/she will initiate the Et Control option or will continue to provide the standard of care depending on the randomization assignment of the subject.

**NOTE:** *Et Control is intended to be used continuously up to and through the emergence phase, and until the subject is disconnected from the breathing circuit.*

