### 6.2.3 Emergence Phase

This phase starts once the clinician stops administering anesthetic agent and the fresh gas flow rate is > 4 l/min for 5 breaths to begin washing out the inhaled anesthetic agent from the patient in preparation for the subject to regain consciousness. When no additional breaths are detected by the Aisys CS, then the patient is disconnected from the anesthesia machine. This phase ends when the subject is finally disconnected from Aisys CS anesthesia machine.

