## 8. DATA ANALYSIS AND STATISTICS

### 8.1 Statistical Analysis Methods

#### 8.1.1 Sample Size Determination

This study is intended to demonstrate that Et Control is non-inferior to the control device in maintaining end tidal anesthetic agent (EtAA) and end tidal oxygen (EtO2) concentrations.

The primary efficacy endpoint is the weighted average per subject of percent duration of EtAA and EtO2 concentrations maintained within the acceptable range for a subject. The acceptable range is specific for each steady state. For EtAA, the acceptable range is defined as +/- the larger of 5% of the steady state concentration or 0.1% v/v for Iso, 0.2% v/v for Sev, 0.6% v/v for Des; and for EtO2, it is +/- 5% v/v. The duration of each steady state will be used as the weight when calculating the weighted average. For EtAA,

$$\text{PercentDuration} = \frac{\sum_j \sum_i t_{ij} I_{ij}}{\sum_j T_j} \times 100\% \quad \text{where } t_{ij} \text{ is the } i^{\text{th}} \text{ duration of EtAA concentration}$$

maintained within the acceptable limit during the  $j^{\text{th}}$  steady state, and  $T_j$  is the total duration of the  $j^{\text{th}}$  steady state.  $I_{ij}$  is an indicator for whether EtAA is maintained within the acceptable limit of  $i^{\text{th}}$  duration in  $j^{\text{th}}$  steady state, which is

$$I = \begin{cases} 1 & \begin{array}{l} \text{if Desflurane and } \Delta\text{EtAA} \leq \max(0.6\%, 5\%X \text{ steady state EtAA}) \\ \text{if Sevoflurane and } \Delta\text{EtAA} \leq \max(0.2\%, 5\%X \text{ steady state EtAA}) \\ \text{if Isoflurane and } \Delta\text{EtAA} \leq \max(0.1\%, 5\%X \text{ steady state EtAA}) \end{array} \\ 0 & \text{otherwise} \end{cases}$$

$\Delta\text{EtAA}$  is the absolute difference between measured EtAA concentrations and steady state EtAA concentration.

Similar definition is used for EtO2 except that acceptable limit is set as 5% v/v.

From the results of the feasibility study, the average percent duration of EtAA and EtO2 concentrations that exceeded the defined acceptable range for the Control Arm was about 13% and about 18%, respectively. In this study, the non-inferiority margin is set at 5% for both EtAA and EtO2, which is about 1/3 of the performance of the Control Arm, i.e., Et Control will be considered non-inferior to the control device if its performance is no worse than that of the control device by more than 5%.

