So the hypotheses on the primary endpoints are:

$$H_0: \mu_{\text{et}} - \mu_{\text{con}} < -5\% \text{ vs } H_1: \mu_{\text{et}} - \mu_{\text{con}} \geq -5\%$$

**Study Title:** Multi-site Anesthesia randomized controlled Study of End tidal control (Et Control) compared to conventional anesthesia Results (MASTER-Anesthesia Trial)  
**Study No:** 123.07-2015-GE5-0002

GE Healthcare

for both EtAA and EtO2, where  $\mu_{et}$  is the percent duration of Et Control with EtAA and EtO2 maintained within the acceptable range, and  $\mu_{con}$  is the percent duration of control device with EtAA and EtO2 maintained within the acceptable range.

Both null hypotheses have to be rejected for EtAA and EtO2 to conclude non-inferiority. So the alpha is set at 0.025 one-sided with no need for multiplicity adjustment, but the power for each hypothesis is set at 0.95 to have an overall power of 0.9 for the study. And the larger sample size calculated for EtAA and EtO2 will be the size of the study.

The results from the feasibility study on the weighted average of percent duration with EtAA and EtO2 maintained within the acceptable range is listed below. The difference between Et Control and control device is assumed to be 50% less than what was observed, and the larger standard deviation observed is used in sample size calculation using the 2-sample t-test method.

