### 8.1.5 Et Control Accuracy

To assess the accuracy of Et Control in maintaining the target EtAA and EtO2 concentrations for each steady state, both mean absolute difference and mean percent difference between measured Et concentrations of AA and the setting values will be calculated, and the mean differences will be summarized for all steady states using descriptive statistics and 95% confidence intervals for each anesthetic agent and overall. The same accuracy analysis will be performed for EtO2. The mean differences will also be plotted against the setting values to assess consistency across the concentration range for each anesthetic agent. Percent of time duration in a steady state will also be assessed; when the percent difference exceeds 5%, 10%, and 15% of the setting values.

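### Maximum agent deviation is scored as a percent of each steady state's own mean with agent-off washout left in, so the washout tail would usually set the subject's score

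*Combined protocol and SAP*

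**What the plan says.** For agent, section 8.1.4.1 puts average and maximum deviation on the scale of percent of the steady-state mean; for oxygen it uses v/v. For maximum deviation, "the maximum of all steady states for a subject is taken for analysis", and the arms are compared by the Wilcoxon rank sum test.

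Section 8.1.5 assesses Et Control accuracy over all steady states. Both an absolute difference and a "mean percent difference between measured Et concentrations of AA and the setting values will be calculated", together with the share of time on which the difference exceeds 5%, 10% and 15% of the setting.

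Steady states come from Appendix 2. A setting change is significant if EtAA moves by 0.9, 0.31 or 0.17 %v/v (desflurane, sevoflurane, isoflurane) within 2 minutes (step 2). A stable period needs a slope below 0.2 %v/v per minute for 2 minutes (step 3). Its level is the average of all points until the next significant change (step 4).

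Emergence is inside the data window. Under section 6.2.2, "Et Control is intended to be used continuously up to and through the emergence phase". On emergence, section 6.2.3 says: "This phase starts once the clinician stops administering anesthetic agent". Section 6.1.1 says that evaluable "data ends when the patient is finally disconnected from the Aisys" breathing system, and section 6.1.2 gives the same end point for the Control Arm.

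**The concern.** Stopping the agent is a setting change that moves EtAA by more than the step 2 threshold. As washout slows, its lower end meets the step 3 slope rule while the concentration is still falling towards zero. That stretch becomes a steady state whose mean is a small fraction of the maintenance level. Dividing by that mean turns a change of a few tenths of a %v/v into a deviation of 50% or several hundred percent. Taking the subject's maximum then selects it.

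At stake is what the comparison measures. If most subjects' maxima come from the tail, the ranks order subjects by how fast they wash out and how long they stay connected. Faster washout gives a worse score, which is the reverse of what a reader would take from the label. Time from end of surgery to last breath is itself an endpoint (sections 3.4.3 and 8.1.4.4), so an arm difference there could reappear as a difference in maximum deviation.

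Section 8.1.5 has a related, conditional problem. If the logged EtAA target is zero or off after agent is stopped, percent difference from the setting cannot be computed for those states.

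**Working it through.** The plan gives no figure for maximum deviation or for accuracy in emergence, so there is nothing of that kind to reproduce. Its sample size depends on the primary endpoints only and does reproduce: a two-sample t-test with SD 16, expected difference +3, margin 5, one-sided alpha 0.025 and power 0.95 gives 105 per arm, and 105/0.85 = 123.5, rounded up to 124.

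**Inputs from the documents.** 1 MAC = 6.0, 2.1 and 1.15 %v/v for desflurane, sevoflurane and isoflurane (footnote in section 2.1); the Appendix 2 thresholds above.

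**Assumptions, not in the documents.** Exponential washout c(t) = c0·exp(−t/τ) from c0 = 1 MAC; τ = 1, 2 or 4 min; disconnection at T = 5, 8 or 12 min after agent stop; 12 breaths per minute. That makes 27 settings.

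**Is the agent stop a significant change?** The fall in 2 minutes is c0·(1 − exp(−2/τ)). It is smallest at τ = 4: 2.36, 0.83 and 0.45 %v/v against thresholds of 0.9, 0.31 and 0.17. It is always significant. Section 8.3 gives 0.15 for isoflurane in a related rule; the result is the same with either value.

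**When does the tail become a steady state?** The slope is c/τ, so stability starts when c = 0.2τ, at t0 = τ·ln(c0/(0.2τ)). The tail qualifies if T − t0 ≥ 2 min.

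**How large is its maximum deviation?** With x = (T − t0)/τ, the tail mean is 0.2τ·(1 − exp(−x))/x. The largest deviation is at the first point, so maximum deviation/mean = x/(1 − exp(−x)) − 1. For x = 1 this is 58%; for x = 2 it is 131%.

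**Example.** Sevoflurane, τ = 2, T = 8: t0 = 2·ln(2.1/0.4) = 3.32 min; x = 4.68/2 = 2.34; ratio = 2.34/0.904 − 1 = 159%. On a breath-by-breath grid the tail starts at 0.40, has mean 0.155, and deviates by at most 0.242 %v/v, which is 156% of its mean. With T = 12 instead, the figure is 334%.

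**All 27 settings (breath grid).**

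| Agent | Tail qualifies | Maximum, % of tail mean | Maximum, % of 1 MAC |
|---|---|---|---|
| Desflurane | 5 of 9 | 57–732 | 2.6–4.8 |
| Sevoflurane | 7 of 9 | 59–828 | 5.7–21.4 |
| Isoflurane | 9 of 9 | 50–891 | 12.1–44.3 |
| All | 21 of 27 | 50–891 (median 206) | 2.6–44.3 |

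**Maintenance comparator (assumed).** A 90-minute state of 1080 breaths, autocorrelation 0.9 and breath SD 2%, 3% or 5% of the mean has a median maximum deviation of 6.3%, 9.5% or 15.8%. In all 21 qualifying settings the tail exceeds these values.

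**Would a MAC scale alone cure it?** No. As a percent of 1 MAC, the tail still exceeds 6.3%, 9.5% and 15.8% in 15, 13 and 6 of the 21 settings. All of these are sevoflurane (6, 4, 1) or isoflurane (9, 9, 5).

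**Wider assumptions.** With τ from 1 to 8 min, a slow residual of 0%, 5% or 10% of the starting level, and data ending at 6, 10 or 15 min, the tail qualifies in 117 of 135 cases. The 18 failures are all desflurane. The deviation runs from 23% to over 1000% of the tail mean.

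**Accuracy.** Percent difference is (measured − setting)/setting. With a setting of 0 the ratio does not exist, and the limits of 5%, 10% and 15% of the setting all become 0. The affected time is then either lost or counted as exceeding every limit, depending on how the program is written. Measured minus setting in %v/v stays defined.

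**The case against.** The washout and maintenance parameters are all assumed, and the maintenance model may be too quiet. Appendix 2 step 4 folds non-significant setting changes into one state, which widens real deviation. In the feasibility study, control subjects were outside limits for 11.3% (section 1.2.3) or about 13% (section 8.1.1) of the time. Under normality with a limit of 0.2/2.1 = 9.5% of the mean, that implies a breath SD of about 6% and a maximum near 19% to 20%. This stands. It narrows the gap: 50% against 20% is 2.5-fold, and the wider set's 23% is barely above 20%. A reader might infer that the tail always supplies the maximum, or dwarfs maintenance by a fixed multiple. The documents support neither, and some tails, mainly desflurane, never qualify.

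Appendix 2 calls itself a high-level description, so the program may already exclude emergence. If so, the plan should say so; the text as it stands does not.

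A zero or off target is an inference from sections 6.2.2 and 6.2.3. The device description in section 2.1.2 is partly missing from the public text, so its silence cannot be held against the plan. A reader might infer that percent accuracy as a whole is undefined. That goes too far: only agent-off states would be affected, and section 8.1.5 also plans absolute differences.

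The consequence is limited. Maximum deviation is not listed in section 3.4.2, although accuracy is. Neither is in the test sequence of section 8.1.2 or the pass criterion of section 8.4. Average deviation is weighted by duration, so a few tail minutes count for little there. The rank test blunts extreme values, but it does not help when most scores come from the tail.

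**Conclusion.** The concern holds for the agent maximum. Followed as written, sections 8.1.4.1, 6.1.1 and 6.1.2 and Appendix 2 let an agent-off washout tail enter as a steady state with a small divisor. Under the assumed washout it qualifies in 21 of 27 settings, at about 50% to 890% of its own mean, and would usually be the subject's maximum. How often this happens in practice depends on washout times and disconnection times that the documents do not give.

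The percent scale is not the only fault. Leaving agent-off states in the data also matters, because a fixed MAC scale alone keeps the tail as the maximum in many sevoflurane and isoflurane settings.

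The accuracy part is conditional on a zero or off target being logged, and is confined to percent difference and the 5%, 10% and 15% time shares for those states.

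A reader might extend the small-divisor argument to oxygen or to the primary endpoints. It does not reach them: oxygen deviation is in v/v, and the primary EtAA limit has an absolute floor of 0.6, 0.2 or 0.1 %v/v. This should be fixed before programming, but it does not threaten the trial's conclusion.

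**What to change.** In section 8.1.4.1, compute maximum and average agent deviation only over steady states before agent is stopped, and define agent-off from the logged settings. Report both also on a fixed scale, either %v/v or a fraction of 1 MAC.

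In section 8.1.5, compute percent difference and the 5%, 10% and 15% time shares only for steady states with a non-zero EtAA target. Report agent-off time in %v/v only, and state what target value the log holds once agent is stopped.

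The cost is plan wording and a filter in the extraction or analysis program. The downside is that emergence deviations are reported separately and no longer enter the stated percent-of-mean maximum. Sample size (124 per arm, 248 in total), the primary analysis and clinical conduct are unchanged.
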